7.4 Missing Data

Because the efficacy data are collected twice only, and the endpoint analyses will be baseline adjusted ANCOVA or single point assessments only, there will be no imputation of missing data. However, to elucidate possible biases this method entails, baseline data for patients for whom endpoint data exist will be compared with baseline data for patients who for some reason drop out or are unable to complete both sets of tests. We will also explore if the dropout rate differs between the treatment arms. The extent of missing data will be quantified for each endpoint variable.

We expect few missing baseline covariates and will not employ a strategy to impute missing baseline covariates.

8 Summary of Study Data

The baseline, intention-to-treat population demographics will be presented by columns for each treatment (Placebo, Intravenous iron isomaltoside). All continuous variables will be summarised using the following descriptive statistics: mean \pm standard deviation; median (interquartile range). The frequency and percentages (based on the non-missing sample size) of observed levels will be reported for all categorical measures. All summary tables will be structured with a column for each treatment in the order (Control, Experimental) and will be annotated with the total population size relevant to that table/treatment, including any missing observations.

The sample size of non-missing values for univariable summary statistics may be larger than the sample size of non-missing values in a complete-case analysis used in the primary regression (ANCOVA) analysis.

Table 1

Demographics	Placebo	Intravenous iron
Age – years		
Male gender – no (%)		
Time since HTx – years (IQR)		
Reason for HTx, no (%)		
Ischemic		
DCMP		
GUCH no		
Other no		
Left ventricular ejection fraction		
NYHA functional class, no (%)		
I		
II		
III		
IV		
Body mass index – kg/m ²		

Systolic blood pressure – mmHg

Heart rate – beats per minute

Treatment

Cyclosporine/Tacrolimus

Everolimus

Mycophenolic acid/Azathioprine

Prednisolone

Angiotensin converting enzyme inhibitor

Angiotensin II-receptor antagonist

Loop diuretic

Thiazide

Beta-blocker

Calcium antagonist

Platelet inhibitors

Oral anticoagulants

Proton pump inhibitors

Biochemistry

Haemoglobin – g/l

Creatinine - μ mol/L

Estimated glomerular filtration rate – ml/min/1.73m²

Ferritin – μ g/l (IQR)

Transferrin saturation – % (IQR)

Transferrin receptor (mg/l) % (IQR)

Sedimentation Rate – mm (IQR)

C-reactive protein – μ g/l (IQR)

Total plasma protein – g/l

Troponin T – ng/l (IQR)

N-terminal pro B-type natriuretic peptide-ng/l (IQR)

Ferritin < 30 μ g/ - no (%)

[figure not shown]
Transferrin saturation < 20% - no (%)

[figure not shown]
Ferritin 100-300 μ g/l +Transferrin sat. <20% -no (%)

8.1 Subject Disposition

We will document how many subjects reached the various stages of the trial (the number screened, randomised, reached the 6-month follow-up visit and could be analysed for the primary endpoint), and how many dropped out and for what reasons (death, withdrew consent, failed to show up) according to the following CONSORT diagram:

8.2 Demographic and Baseline Variables

The following baseline variables will be presented:

The summary statistics will be produced in accordance with section 8.

8.3 Treatment Compliance

Because the study intervention consists of a single, intravenous infusion, there is no issue with treatment compliance. The intention-to-treat primary analyses will be performed regardless of whether or not the study drug infusion was completed, but the number of patients who did not receive the intervention will be reported for each group.

9 Efficacy Analyses

9.1 Primary Efficacy Analysis

The primary endpoint, the baseline-adjusted peak oxygen consumption 6 months after the intervention, will be calculated by ANCOVA with treatment allocation and the baseline peak oxygen consumption as covariates according to the intention-to-treat principle, the statistical null-hypothesis being that the baseline-adjusted oxygen uptake does not differ between the two treatment arms. If the primary endpoint is met at a significance level of 0.05, the result will be considered confirmatory of the main research hypothesis.

9.2 Secondary Efficacy Analyses

Secondary, per protocol analysis will be performed for the primary endpoint. Exploratory subgroup analyses will be performed for the six subgroup categories mentioned in the section “Covariates and subgroups. The latter results will be communicated as a forest plot, and the interaction value of the covariates “treatment allocation” and the binary subgroup identifier in question will be reported at a significance level of 0.05.

9.2.1 Secondary endpoints

The baseline-adjusted between-group difference in the change in i) hand grip strength, ii) normally distributed body composition data, and iii) the SF36 score and the visual analogue scale data from the EuroQoL 5D 3L form will be calculated by ANCOVA. The statistical null-hypotheses are that the changes in these characteristics do not differ between patients allocated to iron isomaltoside and patients allocated to placebo.

NT-proBNP, TnT and CRP at six months will be analysed using Mann Whitney U-tests, the statistical null-hypothesis being that the levels of these biomarkers do not differ between the treatment arms. The between-group difference in the proportion of patients with a minimum clinically important improvement, defined as an improvement of 4 points, and the between-group difference in the proportion of patients with a minimum clinically important deterioration, defined as a decrease of 4 points, will be calculated by Chi square tests.

Secondary per protocol analyses will be performed using the same methods as for the intention-to-treat analyses.

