# 6 Study procedures

## 6.1 Table

	Baseline		3 months	6 months
Informed consent	x	Study drug infusion		
Clinical examination	x		x	x
ECG	x			x
Echocardiography	x			
Safety samples 	x		x	x
Serum hCG 	x			
Randomisation	x			
Biobank samples 	x			x
6-minute walk test	x			x
Measurement of peak oxygen consumption	x			x
Hand grip strength	x			x
Body mass composition	x			x
Cognitive function	x			x
Quality of life	x			x
Adverse events		↔x↔		

Haematological parameters, renal function, serum electrolytes, tests of liver damage, TnT, NT-proBNP and CRP are measured routinely in our transplant recipients. In pre-menopausal women only Secondary endpoints (i.e. NT-proBNP, markers of iron metabolism and inflammation).

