#### *Laboratory analyses*

Blood samples will be obtained to determine: Haemoglobin; white blood cell count, platelet count; serum potassium; serum sodium; glucose, glycosylated haemoglobin (HbA1c); creatinine; ALT; bilirubin; albumin; INR; CRP; N-terminal pro-B-type natriuretic peptide (NT-proBNP); total cholesterol; ferritin; transferrin, serum iron and total iron binding capacity. Serum hCG must be evaluated to exclude pregnancy in pre-menopausal females, and repeated prior to study drug infusion if more than 72 hours have passed between screening and study drug administration. Blood for efficacy analyses must be drawn and appropriately labelled and stored for later analysis.

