### 7.1 Assessments of efficacy

Efficacy will be evaluated through a comprehensive assessment of peak oxygen uptake, hand-grip strength, self-assessed quality of life, assessment of cognitive function, and biochemistry. All efficacy assessments will be made prior to study drug infusion and at the end-of-study visit after six months. The results will be reported as baseline-adjusted between-group differences.

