### 7.1.6 Blood samples

---

We will draw blood samples for biobanking at baseline, prior to study drug infusion, and at 6 months. For biobanking, 18 ml blood should be drawn into tubes containing EDTA as the anticoagulant, 6 ml into tubes with citrate as the anticoagulant and 6 ml into tubes without additives. The tubes with EDTA and citrate should be put on ice immediately and be centrifuged at 3700 rotations/min for 20 minutes. The tubes without additives should be left at room temperature for 1-2 hours prior to centrifugation at 3500 rotations/min for 15 minutes. The tubes containing citrate as the anticoagulant should be put on ice immediately. The resulting plasma and serum, respectively, should be stored in multiple aliquots (at least four aliquots of serum and six aliquots of plasma per patient per visit), and labelled with the unique trial subject number, and the letter A signifying baseline, and the letter B signifying the end-of-treatment visit. The samples should be stored at -80 degrees Celsius until analysis.

Blood samples for safety will be collected at baseline, and 6 months after randomisation (end-of-study). These blood samples will be drawn and analysed at the study sites as per clinical routine. Troponin values will be used for endpoint analyses.

NT-proBNP will be assayed on a MODULAR platform (Roche Diagnostics, Basel, Switzerland). Plasma levels of CRP will be determined by a high-sensitivity particle-enhanced immunoturbidimetric assay (Tina-quant CRP [Latex] HS, Roche Diagnostic, Basel, Switzerland). TnT will be assessed using a high-sensitive immunoassay (Roche hs-TnT).

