5.5 Study Variables

Primary endpoint: The primary endpoint, the peak oxygen consumption, will be measured as the three highest ten-second averaged measurements before the termination of exercise. The oxygen consumption is measured in ml/kg/min, meaning that the absolute oxygen uptake (in ml/minute) divided by the patient's weight (in kg) as measured on the day of the test procedure.

Secondary endpoints:

The muscle strength is measured in KG. The baseline-adjusted between-group values will be analysed by ANCOVA, if necessary after log.-transformation of the data.

Quality of life as assessed by the EuroQoL 5D 3L will be assessed as the sum of scores (1-3) for the five questions. The between-group difference will be assessed with the Mann Whitney U-test. Forms with more than one missing value will be discarded, whereas an average value will be imputed for forms with one missing variable. The between-group results of visual analogue scale data, on a scale from 1-100, will be assessed with baseline-adjusted ANCOVA. The scores for the SF-36v2 will be summed up and transformed to norm a based score of (mean \pm standard deviation) 50 ± 10 as recommended for this version. The between-group difference in the physical and mental score components, as well as the sum of the components, will be analysed with baseline-adjusted ANCOVA analyses. If more than 20 % of values are missing, the forms will be regarded as invalid, and the patients with these forms will be excluded from the intention to treat analysis. If 20 % or fewer variables are missing, we will impute mean values derived from the existing values in the same subscore (mental or physical)

6 Sample Size

This trial is designed to assess the effect of intravenous iron on peak oxygen consumption in heart transplant recipients with iron deficiency. We consider an increase in peak oxygen consumption of 1.5 ml/kg/min, equivalent to approximately half a Metabolic Equivalent of Task (MET), to represent a clinically meaningful improvement. An increase in O₂ consumption of 1.5 ml/kg/min is approximately 6 % of the baseline maximal oxygen consumption in our heart transplant recipients.

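### NT-proBNP, troponin T and CRP are tested on the six-month value alone although baselines are collected and the protocol points to adjustment; the test is valid, but a baseline-adjusted rank ANCOVA would be more efficient if the two values correlate

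*SAP*

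**What the plan says.** SAP 9.2.1 and Protocol 10.5 (key secondary endpoints) use the same words: "NT-proBNP, TnT and CRP at six months will be analysed using Mann Whitney U-tests". The null hypothesis in both concerns the marker levels in the two arms.

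Baseline values are collected:
- The footnote to the Protocol 6.1 schedule, attached to safety samples that are drawn at baseline among other visits, says "TnT, NT-proBNP and CRP are measured routinely in our transplant recipients".
- The baseline laboratory list in Protocol 6.2.1 includes "CRP; N-terminal pro-B-type natriuretic peptide (NT-proBNP); total cholesterol; ferritin; transferrin, serum iron and total iron binding capacity". Troponin T is not in that list.
- Protocol 7.1.6 takes safety bloods at baseline and six months and adds: "Troponin values will be used for endpoint analyses".
- SAP section 8, Table 1, reports all three markers at baseline.

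Two protocol statements point towards adjustment. Section 7.1 includes "self-assessed quality of life, assessment of cognitive function, and biochemistry" in efficacy, places all efficacy assessments before infusion and at six months, and says: "The results will be reported as baseline-adjusted between-group differences". The general paragraph of section 10.5 assigns continuous efficacy variables to t-tests and to baseline-adjusted ANCOVA, with log-transformation where the assumptions require it.

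The SAP leaves room for unadjusted tests. Section 7.3 ties adjustment to what is specified for each endpoint, and section 7.4 foresees that some endpoints are assessed at a single time point.

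**The concern.** The three markers are most of the named evidence for the secondary objective on myocardial disease and inflammation; the only other marker item under it is a general one, inflammatory and vasoactive peptides. Protocol 10.1 and SAP section 6 raise enrolment from 88 (2 × 44) to 100, partly for drop-out and partly to give secondary endpoints a better chance of significance. A baseline value already in hand can serve that second aim without further patients, and the planned test does not use it.

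There is also a question of which text governs. Protocol 7.1 and the general paragraph of 10.5 lead a reader to expect adjusted results for these markers; the endpoint-specific paragraph of 10.5 gives an unadjusted test. The SAP repeats the latter without comment, and SAP section 12 mentions no difference in method.

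**Working it through.** **The plan's own figure.** The only stated sample size is for peak oxygen consumption: difference 1.5, SD 2.5, two-sided 5%, 80% power. Then n = 2 × (1.960 + 0.842)² × 2.5² / 1.5² = 43.6, so 44 per arm, which reproduces. Nothing comparable is given for the markers.

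**Assumptions, none of them from the documents.** True 25% reduction (ln 0.75 = −0.288), log-SD 0.9, so a shift of 0.288 / 0.9 = 0.320 SD; 44 per arm with complete data; two-sided 5%; r from 0 to 0.8. The three markers need not share one r.

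**Methods compared.**
- Mann-Whitney on the six-month value.
- Rank ANCOVA: rank(six-month) = a + b × treatment + c × rank(baseline) + error, testing b = 0.
- Log-ANCOVA: the same model on log values.

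**Hand check.** Power is about Φ(z − 1.960).
- Mann-Whitney: z = 0.320 × √22 × √(3/π) = 1.465, giving 31%.
- Rank ANCOVA divides z by √(1 − s²), where s is the rank correlation (6/π) × arcsin(r/2) = 0.288, 0.483 and 0.683 at r = 0.3, 0.5 and 0.7. This gives z = 1.530, 1.673 and 2.006, hence about 33%, 39% and 52%.

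**Simulation, normal logs** (20,000 to 80,000 trials per cell). Mann-Whitney lay between 30.1% and 31.3% throughout.

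| r | Rank ANCOVA | Log-ANCOVA |
|---|---|---|
| 0 | 30.5% | 31.6% |
| 0.2 | 31.1% | 32.4% |
| 0.3 | 32.3% | 33.8% |
| 0.35 | 33.4% | 35.2% |
| 0.4 | 34.7% | 36.3% |
| 0.5 | 37.7% | 40.1% |
| 0.7 | 50.0% | 54.3% |
| 0.8 | 63.1% | 68.6% |

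Mann-Whitney with 50 per arm gives 33.6%. Rank ANCOVA with 44 per arm reaches that between r = 0.35 and 0.4, so from there the baseline is worth about as much as the 12 extra patients.

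**Other assumptions, same pattern.**
- Log-SD 0.6, r = 0.3 / 0.5 / 0.7: Mann-Whitney 58%; rank ANCOVA 61%, 69%, 84%.
- Log-SD 1.2, same r: 19 to 20%; 20%, 24%, 31%.
- Shift of 0.6 SD, same r: 78%; 80%, 87%, 96%.
- Heavy-tailed logs (t with 3 df, independent at each visit), r = 0 / 0.3 / 0.5 / 0.7: Mann-Whitney 52 to 53%; rank ANCOVA 52%, 55%, 61%, 73%; log-ANCOVA only 37%, 38%, 42%, 48%. This is why the rank version should decide.
- 20% of values at a detection floor, r = 0 / 0.3 / 0.5 / 0.7: Mann-Whitney 29 to 30%; rank ANCOVA 29%, 31%, 36%, 47%.

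**Type I error across these distributions.** Mann-Whitney 4.7 to 5.3%; rank ANCOVA 4.8 to 5.3%; log-ANCOVA 4.3 to 5.3%.

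**Missing baselines** (normal logs; Mann-Whitney keeps all 44 per arm).
- 2 per arm missing: rank ANCOVA 31%, 36%, 48% at r = 0.3, 0.5, 0.7; at r = 0, 29.4% against 30.4%.
- 4 per arm missing: 30%, 35%, 46%; at r = 0, 27.6% against 30.0%.

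**The case against.** The best defence is that the SAP makes no error. It follows the endpoint-specific rule of Protocol 10.5 word for word, and SAP 7.3 and 7.4 allow single-time-point tests. The marker null concerns levels, whereas the ANCOVA endpoints have a null about changes, and Mann-Whitney fits the former. It also keeps every patient with a six-month value under the no-imputation rule. All of this stands, and it shows that the planned test is valid; it does not show that it is the most efficient choice.

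It can also be said that Protocol 7.1 is a short overview that one clarifying line would settle, that rank ANCOVA appears in neither document, and that power stays low either way in the main scenario. These points limit the weight. They do not remove the mismatch, because the general paragraph of 10.5 also names baseline adjustment.

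A reader might infer more than the documents support:
- That the SAP contradicts itself or inflates type I error. Sections 7.3 and 7.4 and the simulated error rates say otherwise.
- That SAP 9.3 treats exploratory markers better. It offers ANCOVA or t-tests, does not say that the ANCOVA is baseline-adjusted, and may itself cover CRP as an inflammatory parameter.
- That the same gain applies to the EuroQoL 5D sum score, for which SAP 5.5 says: "The between-group difference will be assessed with the Mann Whitney U-test". The wording sits equally badly with Protocol 7.1, but no calculation here covers that score.
- That rank ANCOVA costs nothing. That is nearly true only with complete baselines.

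**Conclusion.** The point holds as an optional improvement in efficiency and consistency for three secondary endpoints. The planned Mann-Whitney tests are valid and pre-specified, and the primary analysis and its sample size are unaffected.

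The size is conditional on a correlation that the documents do not report. Under the stated assumptions the gain is negligible below r of about 0.2, about 2 points at r = 0.3, 7 at r = 0.5 and 20 at r = 0.7. With complete baselines, rank ANCOVA was never more than about 0.5 points below Mann-Whitney. With 4 baselines per arm missing, the loss at r = 0 is about 2 to 3 points and the gain at r = 0.3 disappears; SAP 7.4 expects few missing baseline covariates. Confidence in the direction is good; confidence in the size is limited by the assumed inputs.

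**What to change.** Before database lock:
1. In SAP 9.2.1, make rank ANCOVA (ranked six-month value on treatment and ranked baseline) the deciding test for NT-proBNP, TnT and CRP.
2. Report the log-ANCOVA ratio of geometric means with 95% CI as a descriptive estimate, and state in advance that the rank p-value decides.
3. Keep Mann-Whitney as a pre-named sensitivity analysis, reported in all cases, with no data-driven switch.
4. List the change in SAP section 12 as a difference from Protocol 10.5.
5. Reconcile Protocol 7.1 with both the general and the endpoint-specific paragraphs of 10.5. This is needed even if Mann-Whitney is kept.

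Cost: no new data or visits. Protocol 10.4 allows changes until the day of database lock and asks for deviations to be described and justified in the Clinical Study Report. Patients without a baseline value drop out of the adjusted model, so their number should be reported per marker. Each marker now has three analyses, and the rank p-value and the log-ANCOVA interval can disagree on significance: in about 6 to 11% of simulated trials with normal logs and 19 to 29% with heavy tails (r = 0 to 0.7). Naming the deciding test in advance deals with that.

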9.3 Exploratory Efficacy Analyses

Exploratory analyses of between-group differences in inflammatory parameters and parameters pertaining to iron metabolism, such as Hepcidin, Interleukin 6 and the ferritin index will be performed by ANCOVA or repeated test t-tests, if necessary after log-transformation to meet the requirements of the test.

10 Safety Analyses

Safety analyses will include tabulation of type and frequency of all adverse events. Any value of safety laboratory parameters outside normal ranges will be identified. The final report will include the absolute number of adverse and severe adverse events in each group. The results will be reported for the Safety Population only. The summary statistics will be produced in accordance with section 8.

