### **10.5 Statistical analysis**

---

All statistical tests will be performed using a two-sided 5 % level of significance. Continuous efficacy variables will be analysed using independent T-tests for comparisons between the treatment arms and baseline-adjusted ANCOVA for difference in changes. If necessary, values will be log-transformed to meet the assumptions of the tests. All analyses will primarily be analysed according to the intention-to-treat principle. Between-group differences in ordinal categorical variables, such as NYHA class, will be analysed using ordinal logistic regression, whereas the count variables will be assessed by Poisson regression. Demographic, efficacy and safety data will be summarised by treatment group using means, minimums, medians, maximums, interquartile ranges and standard deviations for continuous variables and frequency counts and percentages for categorical variables.

Per protocol analyses will be performed using the same methods as for the intention-to-treat analyses.

**The primary endpoint**, the baseline-adjusted between-group difference in peak oxygen consumption, will be calculated by ANCOVA according to the intention-to-treat principle, the statistical null-hypothesis being that the baseline-adjusted oxygen uptake does not differ between the two treatment arms. Secondary analyses will be made according to the per-protocol-principle.

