4.2 Endpoints

The primary endpoint is the baseline-adjusted peak oxygen consumption as measured on a treadmill exercise test 6 months after study drug administration.

Secondary endpoints:

- The number of patients with absolute or functional iron deficiency
- Muscle strength as measured by a dynamometer hand-grip device
- Body composition
- Cognitive function as assessed by the Cambridge Neuropsychological Test Automated Battery
- Quality of life as assessed by the SF-36 and 5D EuroQoL questionnaires
- N-terminal pro-B-type natriuretic peptide (NT-proBNP)
- Cardiac troponin T (TnT)
- C-reactive protein (CRP)
- Inflammatory and vasoactive peptides.

5 Study Methods

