5.1 General Study Design and Plan

This is a balanced, randomised, placebo controlled, double blind, parallel group trial. Eligible patients are randomised 1:1 and allocated to intravenous iron supplement or matching placebo at baseline, after providing written informed consent and performing baseline exams. The patients receive the study intervention immediately after randomisation, and no more than 3 days after performing the baseline tests. The patients then return for efficacy tests 6 months ± 2 weeks after the study intervention.

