10.1 Adverse Events

Serious adverse events and adverse events of special interest; pregnancies and adverse reactions to the investigational medicinal products will be reported with comprehensive narratives.

11 Technical Details

Statistical analyses will be performed in IBM SPSS Statistics version 21 or later.

12 Summary of Changes to the Protocol

This Statistical Analysis Plan differs from the protocol (Version 1.4) only with regard to the detail with which the statistical methods and plans for how results are communicated are presented, and the specification of exploratory subgroup analyses of the primary endpoint.

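### SAP 9.3 allows an undefined repeated test t-test for between-group differences in inflammatory and iron markers; read as a paired test, it cannot test such a difference

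*SAP*

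**What the plan says.** SAP 9.3 states its target as "Exploratory analyses of between-group differences in inflammatory parameters and parameters pertaining to iron metabolism", with hepcidin, interleukin 6 and the ferritin index as examples. It then says these analyses "will be performed by ANCOVA or repeated test t-tests, if necessary after log-transformation to meet the requirements of the test". The SAP does not define the second method, and gives no rule for choosing between the two.

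Other passages bear on the same variables:

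- SAP 5.1: "This is a balanced, randomised, placebo controlled, double blind, parallel group trial". The arms are independent.
- SAP 7.4: "Because the efficacy data are collected twice only". The same sentence describes the endpoint analyses as baseline-adjusted ANCOVA or single-point assessments.
- SAP 4.2 lists "Inflammatory and vasoactive peptides" as a secondary endpoint.
- Protocol 10.5: "Continuous efficacy variables will be analysed using independent T-tests for comparisons between the treatment arms and baseline-adjusted ANCOVA for difference in changes".
- Protocol 7.1, whose list of efficacy assessments includes biochemistry: "The results will be reported as baseline-adjusted between-group differences".
- SAP section 12: the SAP "differs from the protocol (Version 1.4) only with regard to the detail with which the statistical methods and plans for how results are communicated are" set out, apart from specifying the exploratory subgroup analyses.

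**The concern.** The sentence in SAP 9.3 names a between-arm question and then permits a method that, as usually understood, answers a within-arm question. A paired t-test compares 6-month with baseline values in the same patients. Run in each arm it yields two within-arm p-values, and no estimate, confidence interval or test of iron against placebo.

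Three things make this more than a loose phrase:

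- The word *or* leaves the method open marker by marker.
- The protocol names different methods, and the SAP does not declare a departure from them.
- No other SAP section supplies a method for these peptides. SAP 9.2.1 gives CRP a Mann-Whitney test. In Protocol 10.5 the ANCOVA list for key secondary endpoints ends with a catch-all for other normally distributed data. In SAP 9.2.1 that third item has become the SF-36 score and the EuroQoL visual analogue scale.

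At stake is whether a listed secondary endpoint has a fixed, valid between-arm analysis.

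**Working it through.** **1. The plan's own figure.** SAP 9.3 gives no number. The only related figure is the sample size in SAP section 6, which reproduces by the normal approximation:

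n per arm = 2 × (1.960 + 0.842)² × (2.5 / 1.5)² = 2 × 7.85 × 2.78 = 43.6, rounded up to 44.

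It is used here only to choose a group size. The requirement is 44 per arm and the enrolment target is 100, or 50 per arm. The illustration takes the midpoint, (44 + 50) / 2 = 47.

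**2. The possible readings against the other passages.**

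| Reading of the phrase | Tests a between-arm difference (SAP 9.3)? | Method named in Protocol 10.5? | Baseline-adjusted (Protocol 7.1)? |
|---|---|---|---|
| Paired t-test within each arm | No | No | No between-arm result |
| Two-sample t-test on change scores | Yes | No: ANCOVA is named for changes | Through the change score only |
| Slip for independent t-test at 6 months | Yes | Yes, but the words do not say so | No |

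No row is clean. The first is the ordinary sense of the words, and under it the method cannot meet its stated purpose. Under the others the method is workable but the wording is wrong.

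**3. What could follow from the first reading.** The documents give no SDs and no expected change for any marker, so these inputs are assumptions:

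- no drug effect;
- 47 analysed patients per arm;
- the same true change in both arms, d, in SDs of the change score;
- a separate two-sided 5 % paired test in each arm.

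For one arm, the probability of significance is p = P(|T| > 2.013), where T is noncentral t with 46 degrees of freedom and noncentrality d√47. The arms are independent, so the probability that iron is significant and placebo is not is p(1 − p).

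| Common change d | One arm significant, p | Iron significant, placebo not, p(1 − p) |
|---|---|---|
| 0 | 5.0 % | 0.050 × 0.950 = 4.8 % |
| 0.1 SD | 10.3 % | 0.103 × 0.897 = 9.2 % |
| 0.2 SD | 26.9 % | 0.269 × 0.731 = 19.7 % |
| 0.3 SD | 52.1 % | 0.521 × 0.479 = 25.0 % |
| 0.4 SD | 76.6 % | 0.766 × 0.234 = 17.9 % |
| 0.5 SD | 91.9 % | 0.919 × 0.081 = 7.5 % |

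**4. Cross-check by simulation.** With 20,000 runs per setting and d = 0, 0.2, 0.3, 0.4 and 0.5 SD, the last column becomes 5, 19, 24, 19 and 9 % with 44 per arm, and 5, 20, 24, 16 and 6 % with 50 per arm. In the same runs a direct two-sample t-test on change scores rejected in 4.6 to 5.1 %, whatever the common change.

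**The case against.** The best defence is that the phrase is a slip. The sentence itself says between-group, Protocol 10.5 names independent t-tests, Protocol 7.1 promises baseline-adjusted between-group differences, and SAP section 12 declares no change of method. On that view the sponsor meant a two-sample test on changes or at 6 months. ANCOVA, a valid method, comes first in the sentence, and the section is labelled exploratory.

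Much of this stands. A reader might infer that the SAP plans to claim a drug effect from a significant change in the iron arm alone. The documents do not support that: no passage plans separate tests per arm or a contrast of their p-values, and Protocol 7.1 points the other way. A reader might also infer that the false-positive rate is inflated as a matter of fact. That holds only if both arms change over six months. At zero change the contrast sits at about 5 %, and by 0.5 SD it has fallen back to 7.5 %. Nor does the point reach the primary endpoint, which has its own ANCOVA in SAP 9.1 and is the only result the SAP calls confirmatory. CRP is separately covered, and the ferritin index is not a peptide in the sense of the SAP 4.2 item.

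The defence does not rescue the wording. If an independent t-test was meant, the text does not say so, and the choice between two methods remains open. The exploratory label lowers the weight of the evidence, but does not turn a within-arm test into a between-arm one. It also sits uneasily with the listing of these peptides as a secondary endpoint.

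**Conclusion.** The point holds as a defect of specification. SAP 9.3 pairs a between-group target with an undefined method that, on its natural reading, cannot address it. On any reading the wording fails to match Protocol 10.5 and 7.1, with no declared change. The paired reading is an interpretation, though the likeliest one in a parallel-group trial with two efficacy time points.

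The lack of a between-arm estimate under that reading needs no numerical assumption. The illustrative error rates do: they rest on no drug effect, 47 per arm, an equal change in both arms and a contrast of separate paired tests. They run from about 5 % at zero change to a peak near 25 % at 0.3 SD, then down to 7.5 % at 0.5 SD. The sample size and the primary analysis are unaffected. The wording should be corrected before database lock, but it does not threaten the trial's main conclusion.

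**What to change.** In SAP 9.3, delete *or repeated test t-tests*. State that each marker is analysed by ANCOVA of the 6-month value on treatment and the baseline value, both log-transformed where needed, and reported as the between-arm estimate with a 95 % confidence interval. The independent t-test of Protocol 10.5 is an acceptable alternative if it is fixed, marker by marker, before unblinding. A comparison of 6-month values alone would not be baseline-adjusted as Protocol 7.1 promises, which favours ANCOVA. Add that any paired within-arm results are descriptive and not evidence of a treatment effect.

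The cost is one or two sentences. Biobank samples are already scheduled at baseline and 6 months (SAP 5.2), the sample size does not change, and Protocol 10.4 permits amendments to the statistical plan until the day of database lock.
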